Telehealth CBT-L for Veterans using substances

Funding Agency: HSR&D

Principal Investigator: [name]

NCT05338268

Abstract

Loneliness—a subjective emotional state characterized by the perception of social isolation—is a psychosocial factor that is associated with increased mortality, substance use, and is associated with precipitants of relapse among individuals with substance use disorders (SUD). Importantly, there are effective interventions that can be used to decrease loneliness; however, these have not been tested on Veterans with SUD who are lonely.

There are no studies that have tested a loneliness intervention in Veterans with SUD who are lonely, which may neglect a broader impact on mental and physical health. This study is ideally situated to generate new and important knowledge on the association of loneliness and SUD. This study seeks to address a transdiagnostic factor, which may improve engagement with social support thereby reducing substance use. An additional innovative aspect of this study is recruitment being conducted outside the VHA. This may increase access to care among those Veterans who are especially isolated.

We will initially conduct a small single-arm trial ($n = 6$) for further refinement. This trial will allow us to collect feasibility of treatment delivery, and treatment satisfaction and acceptability data to further refine the manual. With the refined manual Veterans with SUD reporting loneliness will be randomized to either CBT-L/SUD ($n = 15$) or CBT-SUD ($n = 15$). We will assess: (1) treatment acceptability, (2) participant adherence to treatment, and (3) therapist fidelity. We will also assess outcome measure completion percentage, means and standard deviations, and level of correlation of repeated measurement of primary loneliness outcomes and secondary substance use outcomes.

List of Abbreviations

CBT-LS: Cognitive-behavioral therapy for Loneliness

SUD: Substance Use Disorders

Contents

Study Protocol.....	5
Protocol Title: Telehealth CBT-L for Veterans using substances	5
1.0 Study Personnel.....	5
2.0 Introduction	7
3.0 Objectives	8
4.0 Resources and Personnel.....	9
5.0 Study Procedures.....	9
5.1 Study Design	9
5.2 Recruitment Methods	11
5.3 Informed Consent Procedures	12
5.4 Inclusion/Exclusion Criteria	12
5.5 Study Evaluations.....	12
5.6 Schedule of Assessments	13
5.7 Data Analysis	14
5.8 Withdrawal of Subjects.....	16
6.0 Protection of Human Subjects.....	16
7.0 References.....	21

Study Protocol

Protocol Title: Telehealth CBT-L for Veterans using substances

2.0 Introduction

Substance use is a significant public health concern. Life expectancy in the United States had increased for over 50 years before slowing more recently and having a three-year decline from 2015-2017.¹ This decline is largely attributed to staggering increases in deaths of despair—drug overdoses, alcohol-related mortality, and suicide.^{1,2} The rate of drug overdoses in 2017 was nearly 5 times higher than in 1999. The death rate from alcoholic liver disease increased 40%, with age-specific increases as high as 158% among adults ages 25 to 34 years.¹ Alcohol is estimated to be involved in nearly one-third of all suicides³ and the number of suicides involving opioids nearly tripled from 1999 to 2014.⁴ The suicide rate among Veterans with opioid use disorders is now quadruple the overall rate of Veterans.⁵

The Veterans Health Administration (VHA) has taken an aggressive and comprehensive approach to respond to substance use-related morbidity and mortality.⁶ This includes decreasing opioid analgesic prescribing, increasing non-pharmacological pain treatment, establishing clinical dashboard tools (e.g., REACHVET, STORM), and increasing access to effective medications for opioid use disorders and opioid overdose reversals among many others.⁶⁻¹⁰ These approaches are significant, and at the same time, developing treatments focusing on novel therapeutic targets are critical in addressing substance use disorders (SUD) as Veterans with SUD continue to suffer from comorbidity and premature mortality. *Social factors, such as loneliness and social isolation, continue to plague people with SUD. Greater emphasis addressing these social stressors are essential to curb substance use-related morbidity and mortality.*

The 21st century has brought advances in technology improving our ability to connect and communicate with people from around the world. Despite advances to improve connection, there has been a global increase in loneliness.¹¹ The same technology aimed at increasing connection may be decreasing it for some.¹² Related social factors such as decreases in household and social network size, marriage rates, and religious affiliation rates are contributing to this through diminished opportunities for social connection.¹³ Deaths of despair also have a large impact on communities through the degradation of social networks and social cohesion.¹⁴ Additionally, with measures aimed at increasing social distancing due to the COVID-19 pandemic, many people have become further isolated, have fewer economic opportunities, and have reduced access to adaptive coping strategies and treatment.^{15,16}

Loneliness—a subjective emotional state characterized by the perception of social isolation¹¹—is a critical social factor that can have a significant impact on substance use. Loneliness is evident across the lifespan and occurs at higher rates among those with psychiatric disorders, people who are objectively isolated, and people with chronic illnesses.¹¹ Among a cohort of over 25,000 Veterans, 44% reported feeling lonely at least sometimes in the last month, with other studies among civilians estimating the prevalence from 20-33%.¹⁷⁻¹⁹ Loneliness has a profound impact on well-being. A meta-analysis of 70 studies found that loneliness increases the odds of mortality by 29% even after accounting for key risk factors.²⁰ Researchers have estimated that the impact of loneliness on mortality is comparable to that of

obesity or smoking 15 cigarettes a day.²¹ Loneliness has deleterious effects on physical and mental health, increasing the risk for a constellation of chronic diseases and the development and exacerbation of psychiatric disorders and substance use.^{22,23} Loneliness is positively associated with suicidal ideation and suicide attempts.²² In a study among Veterans with depression being seen in primary care, loneliness (and not other social connection constructs) were associated with increased depression, endorsement of suicidal ideation, and reduced treatment seeking intentions.²⁴

Loneliness and social isolation are critical clinical endpoints that must be addressed among Veterans with SUD to reduce relapse and preventable deaths. A considerable proportion of individuals with SUD experience loneliness. A vicious cycle among people with SUD develops as social contact becomes less rewarding and stigma distances people with SUD from others, including social support. This social isolation then drives further substance use.²⁵ A study among treatment seeking patients with an opioid use disorder showed that nearly three-fourths of women and over two-thirds of men reported *moderate to severe loneliness*.²⁶ Nearly 40% of people with an alcohol use disorder reported feeling lonely and isolated at least sometimes.²⁷ Loneliness among those with SUD have increased risk of relapse and other negative consequences.²⁸ Relative to patients with SUD who do not report loneliness, those reporting loneliness have lower quality of life and life satisfaction, and more mood disorder symptoms, non-suicidal self-injury, and suicide attempts.²⁸⁻³² Loneliness among individuals with SUD is also associated with greater pain severity and sleep disturbance, two precipitants of relapse.^{33,34} People with SUD report loneliness as an important reason for craving and among the most common reasons for relapse.^{35,36} Loneliness is higher earlier in recovery and predicts shorter length of stay in treatment.²⁸ A qualitative study identified a subgroup of individuals using heroin who were characterized as being more socially disconnected and these individuals have more cognitive barriers to engaging in methadone maintenance (e.g., treatment harms outweigh the benefits) compared to other subgroups.³⁷ *Addressing loneliness among Veterans with SUD can reduce risk factors for relapse or continued use and have a significant positive impact on how a person develops, maintains, and utilizes social support, including treatment seeking—all of which are essential factors in reducing substance use.*³⁸⁻⁴¹

3.0 Objectives

The proposed study will provide critical feasibility and acceptability data on telehealth Cognitive-Behavioral Therapy for Loneliness for SUD (CBT-L/SUD) among Veterans with SUD who report loneliness. We will conduct a small single-arm trial ($n = 6$) for refinement of the intervention and study procedure. With the refined manual, Veterans with SUD reporting loneliness will be randomized to either CBT-L/SUD ($n = 15$) or CBT-SUD ($n = 15$). The specific aims are as follows:

Aim 1: Refine the CBT-L/SUD manual by conducting a one-arm trial among Veterans with SUD who report loneliness ($n = 6$). *We will deliver CBT-L/SUD as part of a small, single-arm trial. This trial will allow us to collect feasibility of treatment delivery, and treatment satisfaction and acceptability data to further refine the manual.*

Aim 2: Randomize participants to receive either CBT-L/SUD (n = 15) or CBT-SUD (n = 15) to assess feasibility and acceptability among Veterans with SUD who report loneliness.

We will assess: (1) treatment acceptability, (2) participant adherence to treatment, and (3) therapist fidelity. We will also assess outcome measure completion percentage, means and standard deviations, and level of correlation of repeated measurement of primary loneliness outcomes and secondary substance use outcomes.

4.0 Resources and Personnel

The study team consists of Drs. [name], [name], [name], [name], research therapists (TBD) to deliver the intervention, and additional research assistants as needed. Research therapists will have at least a master's degree in a counseling/health-related field and prior CBT training. Drs. [name], [name], and [name] will be in charge of executing the scientific objectives of this project. [name] will serve as project coordinator. [name] will assist in IRB documentation, participant payment and tracking, advertising, and conducting eligibility screening. [name] will also complete screening and consent procedures, and complete assessment packets by telephone with participants at baseline, post-intervention and the 30-day follow-ups. Study therapists will deliver the intervention to 36 participants (6 for one arm trial, 30 for small RCT).

5.0 Study Procedures

5.1 Study Design

Study sample: We will initially recruit 6 veterans who screen positive for loneliness and screen positive for active substance use disorder to receive CBT-L. Once these 6 veterans have completed study procedures, we will recruit an additional 30 to be randomized to either CBT-L or CBT-L/SUD. This cohort will be randomized 1:1. The study will take place at the VA Center of Excellence for Suicide Prevention. Participants meeting study eligibility criteria will be enrolled in the one-arm trial to receive CBT-L.

Screening: The project coordinator will screen by phone following a script. Potential participants will provide verbal consent to complete the screening measures. Those individuals meeting eligibility who are interested in participating will be scheduled for a phone-based consent and baseline assessment appointment. Based on our past experience, we expect approximately 25% of all participants who complete the screening to be eligible to and interested in participating. Therefore, we expect to screen no more than 500 participants to reach our sample of 36.

Assessments and Intervention:

Participants will be enrolled following consent and will complete the baseline assessment. Participants will schedule a convenient time for their phone-based intervention sessions. Mid-treatment, post-treatment and 30-day post-treatment follow-up assessments will also be conducted by phone, depending on the phase of the study. Participants will be paid \$40 each assessment completed. The post-treatment assessment will also include an exit interview for participants to describe acceptability of the intervention. Total compensation will be up to \$80 for the pilot phase, and \$120 for the randomized phase.

CBT for Loneliness for Substance Use Disorders (CBT-L/SUD):

The study team recently created a CBT-L/SUD manual (see **Appendix**) starting from a translation of the Kall et al. CBT-L manual as the base.⁴² We then incorporated relevant content and worksheets from the VHA Brief CBT manual and worksheets from CBT-SUD into the CBT-L base.^{43,44} The study team met and discussed ways to integrate content into the CBT-L manual based on our conceptual model, existing literature on substance use and loneliness, and other pertinent content from the VHA Brief CBT manual (e.g., material from behavioral activation) and CBT-SUD manual (examples of negative thoughts; case history).

The full draft of the manual can be found in the **Appendix** with a broad overview of session-by-session content below. CBT-L/SUD is a brief, patient-centered, tailored, one-on-one, 8-session intervention. Each weekly session is 45-60 minutes delivered via telehealth.

Participants will initially be presented with education on activating events eliciting thoughts, behaviors, and emotions that serve to perpetuate loneliness and substance use (i.e., the CBT model). Sessions will then focus on identifying and changing thoughts that contribute to loneliness and substance use. If a participant states “No one wants to be around a drunk like me,” or “my drug use always makes me feel better when I’m alone.” They would be asked to estimate the accuracy of the thought and to dispute it. For example, the original thoughts might be altered to “My buddy called me last week, so apparently he wants to be around me,” “there’s much more to me than just my drinking,” “Shooting up only made me feel lonelier,” and “I enjoyed it more when I got coffee with my brother.” Importantly, CBT-L/SUD encourages participants to test these beliefs in safe, but real-world experiences (e.g., going to get coffee and noting that it reduced loneliness). Exposure and behavioral activation are used to approach avoided behaviors and activities (e.g., social interactions in sober environments) and to increase the participant’s general activity level to improve mood. By increasing activity level, particularly through engaging in pleasant social activities, the participant’s mood may improve by decreasing avoidance, increasing the potential for social contact, reducing risk of substance use, and increasing self-efficacy to engage in such activities without the use of substances. In the final session, the participant identifies ways to cope with loneliness-related problems by identifying strategies, evaluating the potential solutions, and selecting a plan to implement the strategies. This discussion will occur in the context of preventing a return to behavioral inactivation and allowing maladaptive thinking to drive poor coping, further maladaptive thinking, and lack of activity. Throughout the intervention, we emphasize (1) not engaging with individuals who will threaten recovery, and (2) not entering situations or contexts that place them at unnecessarily high risk of use (e.g., meeting people a bar).

- Session 1: CBT Model & Goal Setting
 - Substance use integrated into CBT model; goals also associated with addressing SUD-relevant goals)
- Session 2: Identifying & Challenging Thoughts I
 - Substance-use related thoughts perpetuating loneliness; loneliness-related thoughts perpetuating loneliness
- Session 3: Identifying & Challenging Thoughts II
 - Continued focus on substance use- and loneliness-related thoughts perpetuating substance use and loneliness
- Session 4: Assertiveness Training
 - Teaching effective communication and conflict resolution
- Session 5: Exposure & Behavioral Activation I
 - Incorporating sober activity into exposure and behavioral activation; considering difficulty of exposure when sober

- Session 6: Exposure & Behavioral Activation II
 - Incorporating sober activity into exposure and behavioral activation; considering difficulty of exposure when sober
- Session 7: Problem Solving
 - Developing a plan to remain sober while implementing or practicing CBT skills and increasing social interactions
- Session 8: Review & Relapse Prevention
 - Review is specific to new content, using skills for CBT-L to address and avoid slips and/or relapse

CBT-SUD: We will utilize the DeMarce and colleagues CBT-SUD manual developed for Veterans, which is designed for flexibility and individualization.⁴⁴ In order to maintain consistency with CBT-L/SUD, CBT-SUD will be delivered over 8, ~45-60 minute sessions. CBT-SUD teaches skills to increase awareness and address thoughts, behaviors, and emotions that contribute to the maintenance of substance use. There are three phases of treatment: preparing and planning for change (1 session), cognitive-behavioral strategies (6 sessions), and maintaining change and termination (1 session). Phase 1 includes building support, case conceptualization, building motivation, and orientation to CBT. Phase 2 will continue case conceptualization and building motivation, while introducing and practicing cognitive-behavioral strategies. Sessions include (1) recognizing and dealing with craving, urges, and triggers, (2) learning refusal and listening skills, (3) managing mood, (4) social and recreational counseling, (5) support for sobriety, and (6) problem solving. Phase 3 involves review of skills to help maintain treatment gains and ending treatment. The manual is included as an Appendix.

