5.2 Recruitment Methods

Recruitment and retention procedure: Participants will be recruited using Internet social media websites (e.g., Facebook, craigslist) and select print/web portals that have been used successfully in several large studies. Advertisements will include a link to a study landing page with study information and blank entry forms for interested Veterans to enter contact information through VA Qualtrics on Fedramp, a secure, FISMA-compliant server used across government agencies with an authority to operate with the VA. We plan to enroll 36 participants in the protocol overall.

Participants will also be recruited through a data access request using data from the Corporate Data Warehouse. CDW contains financial, enrollment, demographic, diagnostic, treatment utilization, and other data across Veterans from 1979 to present. All study staff will be trained on accessing these records by [name]. Joint Longitudinal Viewer will be used to access medical records to prioritize recruitment of Veterans with an active SUD. This pre-screening will help reduce Veteran burden and unnecessary contact of Veterans who would not be eligible. Participants identified through this method will be screened using the same criteria as those recruited through social media websites and select print/web portals as described above. Potential participants will be mailed a personalized letter describing the study and provided with a toll-free number so that they can contact study staff if they are interested in participating as well as opt out of future contact. Potential participants may be recruited from other studies that are IRB approved following completion of those other studies or if deemed ineligible. Only study staff that are approved on those studies will recruit those participants. Providers may also refer participants to the study by emailing the research staff/team. Providers will be given the

approved recruitment letters that are provided to Veterans as well as the approved study landing page for information (content can be found on p. 54 of the approved advertising pdf).

Participants will receive compensation for their participation in the study. The compensation amount will be based on the schedule that follows:

Baseline Assessment	\$40
Post-treatment Assessment (w/in a week)	\$40
30-day Assessment (RCT only)	\$40

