Data Monitoring. To ensure adequate participant recruitment and enrollment, each week, the PI will discuss the current number of participants contacted, screened, and enrolled from each site and compare those numbers to the expected based on our preliminary data. If after the first 4 months, it appears we are not reaching our expected number of participants, the PI will discuss potential barriers/obstacles and solutions with the research team and DSMB. Discussions regarding recruitment and enrollment will continue at each meeting with the DSMB to ensure proper implementation of the study.

Data Safety & Monitoring Board. The purpose of the DSMB is to review protocols and consent documents for this study, monitor safety issues throughout the study, provide an overview of the quality of the accumulating data, and provide guidance on interim analyses and stopping rules. The DSMB will be comprised of individuals appointed by the funder (VA Health Services Research & Development) and will have no direct involvement in the study or conflict of interest with the research team conducting the clinical trial. The DSMB responsibilities will include:

- (1) Protect the safety of the participants
- (2) Review, provide approval/disapproval, and provide suggestions to protocols, consent documents, and plans for data safety and monitoring.
- (3) Monitor, provide suggestions, and report on ethical issues regarding protection of human subjects, and advise on ethical issues regarding AEs. The DSMB will coordinate with the PI to report to the IRB any unanticipated problems involving risk. The DSMB will provide potential solutions or other appropriate actions (e.g., altering inclusion/exclusion criteria, changing consent documents).
- (4) Ensure appropriate balance between clinical care, safety, and patient confidentiality.
- (5) Monitor data the progress of the trial. The DSMB will periodically review outcome data for outcomes by treatment condition, including participant recruitment, retention, risks and benefits, and other factors that may affect outcomes. If differences in results

between conditions appear to be clinically significant, the DSMB will review whether the clinical trial should continue with or without further enrollment of new participants.

- (6) Monitor and review any data relevant to quality control and safety.

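### Does a ceiling of 500 screens contradict the plan's own 25% screening yield and its target of 36?

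*Combined protocol and SAP*

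**What the plan says.** Section 5.1 (Screening) gives a rate based on the team's past experience: "we expect approximately 25% of all participants who complete the screening to be eligible to and interested in participating". The next sentence gives the count: "Therefore, we expect to screen no more than 500 participants to reach our sample of 36".

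The target is consistent elsewhere. Section 5.2 states "We plan to enroll 36 participants in the protocol overall", and Section 4.0 splits this into 6 for the one-arm trial and 30 for the randomized trial.

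Screening is not the last step before enrolment. Under Section 5.1, "Those individuals meeting eligibility who are interested in participating will be scheduled for a phone-based consent and baseline assessment appointment", and then "Participants will be enrolled following consent and will complete the baseline assessment".

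On monitoring, Section 6.0 (Data Monitoring) has the principal investigator review the numbers contacted, screened and enrolled each week and "compare those numbers to the expected based on our preliminary data". If recruitment looks short after four months, the consequence is a discussion of obstacles and solutions with the team and the DSMB. Section 5.7 tracks the weekly recruitment rate and completion percentages.

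**The concern.** The word joining the two sentences in Section 5.1 presents 500 as a consequence of 25% and 36. It is not: division gives 144. In reverse, 500 screens at 25% would produce 125 eligible and interested people, and a real need for 500 screens to reach 36 would mean an overall yield of 7.2%.

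This could matter because the study is a feasibility pilot meant to inform a larger trial, and how hard it is to recruit is part of what it should report. If the recruitment review relied on these figures, they could point in opposite directions. An overall yield of 8% would be about a third of 25%, yet 500 x 0.08 = 40 enrolled would still reach 36 within the ceiling.

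**Working it through.** **Inputs.** Target 36 (Sections 4.0, 5.1, 5.2). Share of screen completers who are eligible and interested: 0.25 (Section 5.1). Ceiling: 500 screens (Section 5.1). The documents give no rate for completing screening once started, or for going from eligible and interested to enrolled.

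**1. Can the plan's figure be reproduced?** Expected screens = target / rate = 36/0.25 = 144. Ratio: 500/144 = 3.47. In reverse: 500 x 0.25 = 125, and 36/500 = 7.2%. So 500 does not follow from the two stated inputs alone.

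**2. Does chance variation explain the gap?** Take the smallest n for which a Binomial(n, 0.25) count reaches at least 36 with a given probability:

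| Probability of at least 36 | Screens |
|---|---|
| 90% | 171 |
| 95% | 180 |
| 99% | 197 |
| 99.9% | 218 |

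It does not. These counts also treat 25% as exactly known and assume that everyone eligible and interested enrols.

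**3. What do the steps outside the 25% do?** Let c be the share of people starting screening who complete it, and q the share of eligible and interested people who enrol. Then screens = 36/(0.25 x c x q). The values of c and q below are assumptions, chosen to show the range.

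| c | q | Screens |
|---|---|---|
| 1 | 1 | 144 |
| 1 | 0.9 | 160 |
| 1 | 0.8 | 180 |
| 1 | 0.7 | 206 |
| 1 | 0.5 | 288 |
| 0.8 | 0.8 | 225 |
| 0.54 | 0.54 | 494 |
| 1 | 0.288 | 500 |

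**4. What if the rate itself is lower?** With no other loss, an assumed rate of 20% gives 36/0.20 = 180 screens, 15% gives 240, and 10% gives 360.

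**5. Are the two statements incompatible?** The text sets an upper limit. Every row above is at or below 500, including 144. The statements conflict only if 500 is read as the expected count, which is not how it is worded.

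**6. Does anything use 500?** Section 6.0 sets its comparison by preliminary data and does not cite the ceiling. Its four-month review leads to discussion, with no decision rule on screening yield. The weekly recruitment rate and completion percentages in Section 5.7 are calculated from observed counts.

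**The case for a change.** The best case for acting is that a ceiling introduced as a conclusion should follow from its premise plus a stated margin, and none is given. Chance variation at 25% comes nowhere near 500. If post-screening loss alone were the explanation, only 28.8% (36/125) of people already classed as eligible and interested would go on to enrol, and a team expecting that should say so. Section 5.1 also holds the only yield and screening count in the documents, so someone looking for the expected numbers in Section 6.0 would naturally turn there.

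Part of this stands. The step from 25% to 500 is missing, and the limit is generous. The rest does not carry.

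- It does not follow that either the rate or the count must be wrong. Both can hold with a wide limit, or with modest losses at two stages that the 25% does not cover.
- Setting 7.2% against 25% compares enrolled per person screened with eligible and interested per screen completer. These are different fractions.
- The opposite-signals argument needs 500 to be an expected number in the monitoring review, and Section 6.0 does not make it one. A reviewer wanting an expectation has the 25%, which is stated as one and drawn from past experience.
- The available substitutes would be no better founded. A limit of about 180 assumes the rate is known exactly and nobody is lost after screening; at 80% conversion, 180 is merely the expected count. A yield of about 7% would be back-solved from a ceiling and would displace the team's own experience.

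**Conclusion.** No change is needed. The arithmetic behind the concern is right: 36/0.25 = 144, and the ceiling is about 3.5 times that. But 144 is the expected count at a 25% rate with no loss before screening is completed or between screening and enrolment, whereas 500 is an upper limit. The two are loosely linked, not contradictory. How generous the limit is depends on completion and conversion rates that the documents do not give. Under the assumed values shown, the expected count runs from 144 to nearly 500, and the upper end needs heavy losses.

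The missing explanation affects no result. The target stays at 36, the weekly comparison does not cite the ceiling, the four-month review carries no decision rule on screening yield, and the analyses do not use it. The actual yield can be read from the contacted, screened and enrolled counts that the team will already hold, and those will inform a larger trial better than any prior ceiling.
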